6. INVESTIGATIONAL PRODUCT(S)

All investigational products to be used in this study have been manufactured, packaged and labelled by contract manufacturers for ABIVAX, according to GMP standards and are supplied to investigators free of charge.

6.1. Description of investigational treatment

The study treatment that will be administrated to patients enrolled in this Phase IIa study consists of capsules containing ABX464 or its matching placebo given orally once daily for 28 days.

6.2. Description of investigational Product

6.2.1. Active investigational product (ABX464)

The ABX464 investigational medicinal product (IMP) is a hard gelatin capsule intended for oral administration.

For the proposed clinical trial, the IMP consists of size 00 capsules containing 50 mg of ABX464 drug substance in the form of a granulate prepared with a number of common excipients (microcrystalline cellulose, polyvinylpyrrolidone, magnesium stearate and colloidal silica). It is supplied in high-density polyethylene bottles closed with high-density screw caps.

ABX464 will be manufactured by SEPS Pharma (Belgium) and distributed to the sites by SODIA.

SEPS Pharma CTM	SODIA
[name]	[name]
[name]	[name]
Belgium	France

The study drug has to be stored at ambient temperature (< 25°C). The capsule or combination of capsules to be used depends on the dose-level to be administered as per the clinical study protocol.

6.2.2. Placebo

The matching placebo consists of the same hard gelatin, powder-filled capsules (size 00) filled with only the same common excipients (microcrystalline cellulose, polyvinylpyrrolidone, magnesium stearate and colloidal silica) as the active IMP, supplied in high-density polyethylene bottles closed with high-density screw caps.

ABX464 matching placebo will be manufactured by SEPS Pharma (Belgium) and distributed to the sites by SODIA.

SEPS Pharma CTM	SODIA
[name]	[name]
[name]	[name]
Belgium	France

The study drug has to be stored at ambient temperature (< 25°C). The capsule or combination of capsules to be used depends on the dose-level to be administered as per the clinical study protocol.

6.3. Administration and Dosing

6.3.1. Administration of the investigational product

Patients will be dosed with a fixed daily dose of 50 mg that is respectively 1 capsule of 50 mg. In case of dose escalation to 150 mg is recommended then patients will be dosed with 3 capsules of 50 mg every day.

Patients will be orally dosed in fed condition (regular breakfast) with 240 mL of water.

A patient diary, in which the patient should report the number of capsules taken and the intake time, will be given to the patient at baseline. Moreover, this diary will enable the patient to report also potential discomfort or side effects s/he could experience.

6.3.2. Guidelines for treatment postponement and dose modifications

No intra-patient dose escalation/dose adjustment are allowed.

6.4. Method of Assigning Patients to Treatment Arms

All patients will be assigned a unique and incremental patient Identification (ID) number. Patient IDs will be unique (i.e. reallocation of the ID will not be permitted). The format will be a seven-digit number as follows: ABX-country/site number (4 digits) – patient number (3 digits). The latter 3-digit patient number will be assigned according to the patient's order of inclusion in the center.

Patients will be randomized in the ratio 3:1 to either an ABX464 or the placebo arm at Day 0 if s/he fulfils all inclusion exclusion criteria.

Randomization will be performed via e-CRF. The e-CRF will allocate treatment number assignment. Treatment bottles will be allocated at once at Day 0 by SODIA and send by e-mail or fax.

However, depending on the bottles/strength used, the study treatment dispensation will be performed either only once at Day 0 (30-capsule bottles) or at every site visit (5-capsule bottles). In all cases, patient should return his/her used and unused bottles at each study visit for a compliance check.

6.5. Blinding and breaking the study blind

Study drug will be packaged in blinded label bottles. Bottles will be numbered according to a randomized treatment number list. The content of the labeling is in accordance with the required references listed in the Good Manufacturing Practices.

The investigator, study personnel, and study participants are blinded with respect to treatment (i.e., active ABX464 or placebo). Sponsor or delegate will generate the random code list and the corresponding treatment number list.

Investigator could have access to unblinding only in case of medical emergency via specific envelopes. However, as there is no antidote it is highly unlikely that knowledge of treatment would affect the clinical management of the patient.

6.6. Packaging

The IMP consists in hard gelatin, powder-filled capsules (size 00) containing 50 mg of ABX464, supplied in highdensity polyethylene bottles closed with high-density screw caps.

6.7. Storage

ABX464/Placebo capsules will be shipped to the investigational site at ambient temperature. ABX464/Placebo capsules should not be stored above 25°C. DO NOT FREEZE OR REFRIGERATE.

The IMP should not be used beyond the expiration date. Drug supplies are to be stored in a secure, limitedaccess location under the storage conditions required by GCP/GMP guidelines.

6.8. Product Accountability

An accurate and current accounting of the dispensing and return of IMP(s) will be maintained on an ongoing basis by the pharmacist and a member of the study site staff in the Accountability Log and case report form and will be verified by the study's monitor.

6.9. Prior and Concomitant Medication

6.9.1. Background and allowed concomitant treatment

All Patients must be treated by darunavir/ritonavir or darunavir/cobicistat given as a monotherapy for at least 8 weeks prior to baseline. Ritonavir boosted protease inhibitor treatment should be given at the following doses:

- 800 mg of darunavir and 100 mg of ritonavir once a day with food or
- 800 mg of darunavir and 150 mg of cobicistat once daily with food.

This ritonavir boosted protease inhibitor treatment should be continued during the study period until Day 28.

6.9.2. Prohibited prior or concurrent medications

The following drugs are prohibited during the course of the study.

- Other antiretroviral therapies than those part of the study treatments (e.g. NRTIs, NNRTIs,...);
- Drug therapy with immunomodulators or immunosuppressive drugs (such as IL-2, IL-7, intravenous immunoglobulin-IVIG- or IFN) within one month preceding Day 0;
- Drugs that could interact either with darunavir/ritonavir, darunavir/cobicistat or ABX464 should be avoided especially the CYP1A2 substrates (cf. Appendix#2). The following CYP1A2 substrates with a narrow therapeutic margin are prohibited during the whole course of the study (Clozapine, theophylline, ropinirol, warfarin and methadone).
- Use of any investigational or non-registered product within 3 months preceding baseline.

Potential concomitant medications should be kept at constant dose during the course of the study and properly reported in the medical file of the patient and the eCRF.

This information should include the name of the medication (international nonproprietary name), daily dosage, duration, indication and the time of last intake before all PK samplings.
7. PATIENT COMPLETION AND WITHDRAWAL

7.1. Patient Completion

Treatment with ABX464/Placebo shall continue until Day 28, except if a patient fulfils a premature discontinuation criterion (defined below). After ARTs interruption (Day 28), patients will be followed up twice weekly during the first three weeks and then weekly until Viral Rebound/ART resumption criteria are met. Afterwards, specific follow-up visits should be performed every 14 days after ARTs reintroduction until the viral load has returned to undetectable levels.

7.2. Premature trial discontinuation

A patient can be withdrawn at any time from the study for the following reasons:

- Investigator's decision;
- An Adverse Event or an intercurrent condition that preclude continuation of treatment;
- Major protocol violation;
- Patient's decision;
- Withdrawal of consent

A patient who prematurely exits the study before Day 28, for a non-drug related reason, will be replaced (i.e. an additional patient will be randomized and receive the next treatment allocation. This may or may not be the same treatment as the withdrawn patient).

In addition, a patient must be withdrawn from the study, at any time, if s/he presents an increase in transaminases (AST/SGOT and/or ALT/SGPT) or in Alkaline phosphatase $\geq 2.0 \times ULN$.

7.3. Study Discontinuation

All patients, regardless of the completion or premature discontinuation, should perform the ART reintroduction Visit according to the study flow-chart.

7.4. Screen and Baseline Failures

A patient is considered to be a baseline failure if the patient signs the informed consent but withdraws before the screening visit. All potential patients who are screened for enrolment in this study will be listed on the Patient Screening Log/Identification List. Reasons for exclusion will be recorded for potential patients who do not enter the study.

A patient who does not fulfil the randomization criteria at Day 0 will be considered as screen failure. All patient data should be entered in the eCRF including the screen failure data.

8. ADVERSE EVENTS (AE) AND SERIOUS ADVERSE EVENTS (SAE)

The investigator is responsible for the detection and documentation of events meeting the criteria and definition of an AE or SAE. During the study, in case of a safety evaluation, the investigator or site staff will be responsible for reporting AEs and SAEs, as detailed in this section of the protocol.

During the screening period, only adverse event related to the screening procedures will be collected. Adverse events related to the antiretroviral treatments will be reported directly to the concerned pharmaceutical company according to the local process.

Any disease progression will not be reported in the eCRF as an adverse event, but will be documented in the efficacy section.

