8.1. Definition of an AE

Any untoward medical occurrence in a patient or clinical investigation patient administered a pharmaceutical product and which does not necessarily have to have a causal relationship with this treatment.

An AE can therefore be any unfavorable and unintended sign (including an abnormal laboratory finding), symptom, or disease (new or exacerbated) temporally associated with the use of a medicinal product, whether or not considered related to the medicinal product.

Note: The official definition also extends to AEs occurring in the placebo arm. Because of regulatory requirements, events occurring during pre-and post-treatment periods will also be designated as AEs. Therefore, reporting of such events, AEs and SAEs, will commence when the patient is enrolled into the study (date of signature of the informed consent) up until 4 weeks after the end of the treatment visits. The period after discontinuing study drug may be extended if there is a strong suspicion that the drug has not yet been eliminated.

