8.3.2. Pregnancy report

Patients who become pregnant at any time will be immediately withdrawn from participation in the study. All appropriate withdrawal assessments may be performed at the discretion of the investigator.

The investigator will collect pregnancy information on any woman patient or partner of a male patient, who becomes pregnant and their partner while participating in this study. The investigator will record pregnancy information and submit it to ABIVAX or its designee within 24 hours after knowledge of a patient's or partner's pregnancy. The patient or partner will also be followed to determine the outcome of the pregnancy, be it full-term or prematurely terminated. Information on the status of the mother and child will be forwarded to ABIVAX or its designee. Follow-up will normally end 6 to 8 weeks following the estimated delivery date.

While pregnancy itself is not considered to be an AE or SAE, any pregnancy complication or elective termination of a pregnancy for medical reasons will be recorded as an SAE. A spontaneous abortion is always considered to be an SAE and will be reported as such.

The time period for collecting pregnancy information is identical to the time period for collecting AEs, as stated in Section 8.4, Time Period, Frequency, and Method of Detecting AEs and SAEs. Pregnancy information is collected from the signing of informed consent to 4 weeks after the last dose.

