8.4. Time Period, and Frequency of Detecting AEs and SAEs

Clinical Study Protocol

All AEs and SAEs occurring from the time a patient consents to participate in the study until 4 weeks after he or she has completed or discontinued the investigational product must be recorded in the patient's eCRF. Importantly, SAEs will have to be reported, either by email or by Fax, to SIMBEC- ORION within 24 hours of awareness of an SAE.

SIMBEC ORION

[contact]

[contact]

Legislative guidance requires also reporting any **related** SAEs to be reported after the patient finished the study if the investigator becomes aware of them.

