9.3. Safety Analyses

Adverse events will be coded using the standard dictionary (MedDRA) down to the lower level term (LLT).

An overall summary table will be presented (Any adverse event, any treatment emergent adverse event (TEAE), any serious adverse event (SAE), death, any grade 3 or higher adverse events from baseline to the end of Study. This analysis will be conducted on SAF population.

Two periods will be defined for TEAE:

- Any adverse event which occurs or worsens from first dosing to Day 28;
- Any adverse event which occurs after Day 28.

Adverse events will be described by primary system organ class and preferred term. Numbers and percentage of patients, and number of occurrence of adverse event will be presented for:

- TEAE;
- Serious TEAE;
- TEAE leading to drug discontinuation;
- TEAE of grade 3 or 4;
- TEAE for which relationship with the study drug is recorded as possible or probable.

The assessment of safety will be based on the frequency of adverse events (with and without regard to causality) graded according to the "Division of AIDS table for grading the severity of adult and pediatric adverse events" (December 2004) and also, the review of individual values for clinical laboratory data, vital signs and ECG focusing on the detection of abnormal values and PCSAs [potentially clinically significant abnormalities (PCSAs) determined upon investigator considerations].

Adverse events will be tabulated (counts and percents) by group. All adverse events will be listed and the data will be tabulated by body system/organ class. Adverse event tabulations will include all treatment emergent adverse events, which will be further classified by severity, and relationship to treatment and dose level.

Clinical laboratory parameters, vital signs, ECG will be summarized by using descriptive statistics (n, mean, SD, SEM, median, minimum and maximum). Number of patients with at least one abnormal values will be tabulated (counts and percents) for each parameter in summary shift tables, by group and dose.

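### Section 8 limits adverse events in screening to procedure-related ones, while 8.1 and 8.4 require all from consent, so some symptoms may have no pre-dose grade

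*Protocol*

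**What the plan says.** Two collection rules cover the time between consent and first dose.

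- **The narrow rule.** The opening text of Protocol section 8 says: "During the screening period, only adverse event related to the screening procedures will be collected".
- **The broad rule.** Section 8.1 says that "events occurring during pre-and post-treatment periods will also be designated as AEs", gives regulatory requirements as the reason, and starts AE and SAE reporting on the day the consent form is signed. Section 8.4 covers "All AEs and SAEs occurring from the time a patient consents to participate in the study" and makes eCRF entry compulsory up to 4 weeks after the patient has "completed or discontinued the investigational product must be recorded in the patient's eCRF". Section 8.3.2 assumes the same window: "The time period for collecting pregnancy information is identical to the time period for collecting AEs", and it then states that this window opens at consent.

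The analysis rule that relies on these records is in section 9.3. Its first treatment-emergent period is defined as "Any adverse event which occurs or worsens from first dosing to Day 28".

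Section 3.2 gives a screening period of two to four weeks, and section 5.2.1 places the screening visit 21 ± 7 days before baseline. Section 2.1 makes safety against placebo the primary objective.

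**The concern.** An AE unrelated to a screening procedure that starts before Day 0 is left out under section 8 and compulsory under 8.4. Neither section refers to the other. Section 8.4 cannot easily be read as a general rule with section 8 as its exception, because it covers all events and 8.1 gives a reason for including pre-treatment ones.

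This matters because the on-treatment definition in 9.3 has two limbs. An event counts if it is new after first dosing, or if it was already present and got worse. The second limb is a comparison, and one side of it is the severity before dosing. If that severity was never entered, a statistical analysis plan cannot restore it, so this cannot be left to a later document.

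There is also a reporting question. Section 8 covers both AEs and SAEs, but its screening sentence does not say whether it applies to SAEs. A site could reasonably be unsure whether an unrelated SAE in screening has to be reported.

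**Working it through.** The protocol gives no figure to reproduce here. The check sets the passages side by side and works out the length of the window.

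**1. Length of the affected window.** From 5.2.1: 21 − 7 = 14 days and 21 + 7 = 28 days. This agrees with the two to four weeks in 3.2. Against the 28-day treatment period, 14/28 = 50% and 28/28 = 100%. The window is therefore half to all as long as the treatment period.

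**2. What each rule does with an event starting in that window.**

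| Event between consent and Day 0 | Section 8 | Sections 8.1 and 8.4 |
|---|---|---|
| AE caused by a screening procedure | collected | recorded |
| AE unrelated to a screening procedure | not collected | recorded |
| SAE unrelated to a screening procedure | not clear | recorded and reported |

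The second row is a direct contradiction. The third is an ambiguity.

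**3. What pre-dose information exists whichever rule is followed.**

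- Hematology, biochemistry, urinalysis, ECG, vital signs and physical examination are scheduled at both screening (5.2.1) and Day 0 (5.2.2).
- Laboratory values and reference ranges for safety parameters go into the eCRF (5.3.4). Shift tables from baseline are planned (9.3, 9.3.1).
- Examination findings are judged against baseline (5.3.1), and ECG findings against the baseline visit (5.3.3).
- Abnormal findings present at consent that significantly worsen are reportable (8.3.1).

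Measured parameters therefore keep their baseline.

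**4. What is left uncovered.** Symptoms have no equivalent measurement. Medical history is listed only for the screening visit (5.2.1), so it cannot hold a symptom that starts later. The 5.2.1 list has no AE item. Day 0 does include AE reporting and assessment (5.2.2), but nothing there lifts section 8's limit on events that began in screening. Even an AE mark at screening in the 5.1 flow chart would not say which events to record.

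**5. Effect on the 9.3 rule.** Take a hypothetical headache, unrelated to any procedure, that begins after the screening visit and is moderate when reported during treatment.

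- Under 8.4, its earlier severity is on file. If it was mild before dosing, it has worsened and is treatment-emergent. If it was already moderate, it has not.
- Under section 8, the same headache may first enter the eCRF during treatment. Section 8.5 requires its start date and its timing relative to dosing, so it should be recognisable as old. Whether it worsened cannot be read from the record.

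The missing item is therefore the contemporaneous pre-dose entry and grade of an unrelated symptomatic event that begins between the screening visit and Day 0.

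**The case against.** The strongest reply is that the inconsistency has little practical effect. Sections 8.1, 8.3.2 and 8.4 all point the same way, 8.4 is worded as an obligation, and all sites share one eCRF and are monitored (11.1, 11.5). Most sites may simply record everything from consent. That is plausible, but it relies on sites disregarding an explicit sentence at the head of the safety section.

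Other parts of the reply are right, and they rule out stronger readings that a reader might infer.

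- **That no baseline exists.** The protocol does not support this. Laboratory, ECG, vital-sign and examination baselines are taken regardless of the AE collection rule.
- **That a true worsening would go unreported.** Section 8.1 treats an aggravated symptom as an AE in its own right, so a worsening after first dose is reportable even if nothing was logged in screening. What is lost is the earlier grade against which to confirm it.
- **That old events would pass as new.** Section 8.5 requires an onset date and timing relative to dosing for every recorded event, which should identify an earlier start.
- **That the SAE deadline differs between sections.** Sections 8.4 and 8.6 both say 24 hours, and section 8's opening text gives no deadline. The doubt is about which screening SAEs are covered, not how fast they must be reported.
- **That the comparison is biased towards one arm.** Allocation is randomized and blinded (6.4, 6.5), and the affected events precede dosing. Misclassification would be expected in both arms, and no direction is shown.

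**Conclusion.** The contradiction is real and unreconciled, and it should be corrected because safety is the primary objective. It is an inconsistency in data collection; the rule in 9.3 is not itself at fault.

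Its reach is limited to unrelated symptomatic events that begin in the 14 to 28 days between the screening visit and Day 0, at sites that follow section 8, together with doubt over which screening SAEs are reportable. The protocol gives neither a rate for such events nor any indication of how many sites would take the narrow reading, so the number of treatment-emergent classifications affected cannot be estimated.

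With the 21 and 7 patients per dose level in 9.4, one patient is 1/21 = 5% of the ABX464 group and 1/7 = 14% of the placebo group. Those percentages are only the weight of a single patient in any tabulation and should not be read as the size of this defect.

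The conclusion assumes that no site instruction outside the protocol already settles which rule applies.

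**What to change.** Reconcile the sections to one rule:

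1. Delete the screening sentence in section 8, so that 8.1 and 8.4 govern and every AE and SAE is recorded from consent. This also removes the doubt about SAEs.
2. For each event ongoing at first dose, record the onset date and the grade at Day 0.
3. List pre-dose events separately from treatment-emergent ones, and use them as the reference for judging worsening under 9.3.

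Keeping the narrow rule instead would mean rewriting 8.1, 8.3.2 and 8.4, and would still leave 9.3 without a pre-dose grade for these symptoms. Deletion is the smaller change. It costs one sentence and slightly more data entry at screening. No visit or test is added, because AE reporting is already scheduled at Day 0.

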8.1. Definition of an AE

Any untoward medical occurrence in a patient or clinical investigation patient administered a pharmaceutical product and which does not necessarily have to have a causal relationship with this treatment.

An AE can therefore be any unfavorable and unintended sign (including an abnormal laboratory finding), symptom, or disease (new or exacerbated) temporally associated with the use of a medicinal product, whether or not considered related to the medicinal product.

Note: The official definition also extends to AEs occurring in the placebo arm. Because of regulatory requirements, events occurring during pre-and post-treatment periods will also be designated as AEs. Therefore, reporting of such events, AEs and SAEs, will commence when the patient is enrolled into the study (date of signature of the informed consent) up until 4 weeks after the end of the treatment visits. The period after discontinuing study drug may be extended if there is a strong suspicion that the drug has not yet been eliminated.

